## **Protocol NCT02413996 clinicaltrials.gov**

**Document Date: March 6, 2014**

# **Title: Effects of early Virtual Reality-based Rehabilitation in Patients with Total Knee Arthroplasty: a randomized controlled trial**

## **AIM**

We aim to compare the efficacy of early rehabilitation with virtual reality (VR) via the Virtual Reality Rehabilitation System (VRRS) versus traditional rehabilitation in improving functional outcomes after primary TKA.

## **METHODS**

We will design a two-armed, single-blind, parallel, and superiority randomized controlled trial (RCT). The protocol is approved by the San Raffaele Hospital Ethic Committee in Milan (06/03/2014), registered with clinicaltrials.gov (NCT02413996) and strictly follow good clinical practice guidelines and the tenets of the Helsinki Declaration.

Informed, written consent will be obtained prior to participation. The study reporting followed the CONSORT statement and its extensions .

Subjects will be allocated to treatment group according to a simple computer-generated randomization chart. An independent physician of the rehabilitation ward will assign the subjects to interventions. Assessors will be blinded to the interventions; due to the nature of the interventions, blinding of patients and physiotherapists will be impossible to maintain. An independent consultant will provide the statistical analysis.

We firstly expected to enroll 142 patients based on a pilot small study. However, in agree with our ethical committee, we subsequently amended the sample size according to a recent trial  based on a similar PICO (participants, interventions, comparisons, outcomes) methodology. The primary outcome will be the visual analogue scale (VAS) for pain score (0 to 100 points, wherein 0 denotes no pain). Based on an expected effect at 10 days in the control group of a reduction of 20.4 points on the VAS score, we assumed a common standard deviation (SD) of 25.8, a 5% type I error and a 10% type II error and a significant absolute difference of 20.3 points between the experimental and the control group while taking into account a 20% dropout rate from the whole sample. For this, a total sample size of 84 subjects will be planned.

## **Study setting and Participants**

Participants will be recruited at the Rehabilitation Department, IRCCS Orthopedic Institute Galeazzi, Milan. Eligible participants will be adults between 45 and 80 years old who had undergone primary unilateral TKA for knee osteoarthritis and given written, informed consent to participate in the study. Exclusion criteria will be: previous orthopedic surgery on the same side (e.g., hip arthroplasty), unstable health condition (e.g., heart or lung disease), pregnancy, assumption of psychotropic drugs.

## **Interventions**

Subjects will be randomly allocated 3-4 days after TKA to one of two rehabilitation groups: experimental (VR rehabilitation) or control (traditional rehabilitation). In addition, both groups will perform passive knee motion on a Kinetec® knee continuous passive motion system (Rimec, Chions, Italy) and functional exercises (stair negotiation and level walking) daily for 60 minutes on at least 5 days.

## **Outcomes**

The primary outcome will be the absolute change in pain score as measured in 100 mm on a VAS. The secondary outcomes will be: knee disability as assessed by the Western Ontario and McMaster Universities osteoarthritis index (WOMAC), which consists of 24 items divided into 3 subscales investigating pain, knee joint stiffness, and physical function; health-related quality of life (HRQoL) as assessed by the EuroQol five-dimensional (EQ-5D) questionnaire; the global perceived effect (GPE) as assessed by the GPE score; the Functional Independent Measure (FIM) as assessed by the FIM questionnaire; the frequency of medication assumption; the isometric strength of the quadriceps and hamstring muscles as assessed using a dynamometer, the knee active range of movement (ROM) measured by a goniometer and the proprioception assessed using the stabilometric platform of the Virtual Reality Rehabilitation System (VRRS). In particular, we will measure the percentage value of similarity between the trajectory points of an ideal healthy person's and the patient's center of pressure movement during the reaching test, a different task respect to the proprioceptive exercises proposed in the training of the experimental and control groups. All outcomes will be recorded at baseline and then at discharge (around 10 days after surgery).

## **Statistical methods**

Demographic characteristics will report absolute and relative frequencies for categorical variables, and as mean with standard deviation (SD) for continuous variables. We plan to analyze continuous variables testing each outcome assessment with the Shapiro-Wilk test, and to use parametric methods for significance testing (i.e., t-test). Chi-square tests will be used to assess significant associations between categorical variables. In addition, we plan to apply a multivariate analysis of covariance (ANCOVA) with decrease in VAS as response variable to adjust for demographic characteristics (i.e., patient gender and age), and for baseline VAS pain scores. All analyses will be performed by an independent researcher using STATA statistical software, version 15.

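### Two tests are planned for the primary VAS change, an unadjusted t-test and an ANCOVA, and the plan does not say which one decides superiority

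*Combined protocol and SAP*

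**What the plan says.** The Methods section describes a "two-armed, single-blind, parallel, and superiority randomized controlled trial (RCT" trial with VAS pain as its one primary outcome. The Outcomes section defines that outcome: "The primary outcome will be the absolute change in pain score".

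Statistical methods then applies two analyses to it:

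- For continuous variables in general, after a Shapiro-Wilk test, the plan is "and to use parametric methods for significance testing (i.e., t-test".
- For VAS alone: "In addition, we plan to apply a multivariate analysis of covariance (ANCOVA) with decrease in VAS as response variable". The covariates are gender, age and baseline VAS.

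Neither analysis is called primary, confirmatory, supportive or sensitivity.

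The sample size in Methods rests on "a significant absolute difference of 20.3 points between the experimental and the control group" and "we assumed a common standard deviation (SD) of 25.8", with 5% type I error, 10% type II error and 20% dropout, giving 84 patients. It uses no covariate or baseline correlation.

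Continuous secondary outcomes get the t-test only, although "All outcomes will be recorded at baseline and then at discharge". The plan does not say whether those t-tests compare changes or discharge values.

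**The concern.** A superiority trial with one primary outcome needs one test, named in advance, that decides the claim. Here two valid tests of the same hypothesis are planned without a rule for choosing between them. They are correlated but not identical, so they will sometimes fall on opposite sides of 5%.

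Two things are at stake. First, if either result could support the claim, the type I error would exceed the stated 5%. Second, even if nobody chooses after the fact, a reader faced with two conflicting results could not tell which one was planned.

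A lesser point concerns the continuous secondary outcomes. Their baselines are collected but not used for adjustment. The t-test is valid there under randomisation, so this is precision forgone and not an error.

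**Working it through.** **1. The plan's own figure.** Inputs from Methods: difference 20.3, SD 25.8, 5% type I error (taken as two-sided; sidedness is not stated), 90% power, 1:1 allocation assumed.

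n per arm = 2 × (1.960 + 1.282)² × (25.8/20.3)² = 2 × 10.51 × 1.615 ≈ 33.9, so 34 per arm and 68 in total. Dividing by 0.8 gives 85. The t-based calculation gives 35 per arm, and 70 × 1.2 = 84 exactly. The planned 84 is therefore reproduced by an unadjusted two-mean calculation. That fits the t-test, but it does not designate it.

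**2. Completers.** 84 × 0.8 = 67.2, taken as 34 against 33.

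**3. Why the two tests differ in precision.** Let s_B and s_F be the SDs at baseline and discharge, and r their correlation.

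- Variance of the change: s_B² + s_F² − 2r·s_B·s_F
- ANCOVA residual variance: s_F²(1 − r²)
- Difference: (s_B − r·s_F)², which is never negative

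With equal SDs the ratio of ANCOVA to change-score variance is (1 + r)/2. Against a comparison of discharge values it is 1 − r².

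| r | ANCOVA / change | ANCOVA / discharge value |
|---|---|---|
| 0.2 | 0.60 | 0.96 |
| 0.3 | 0.65 | 0.91 |
| 0.5 | 0.75 | 0.75 |
| 0.7 | 0.85 | 0.51 |

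**4. Simulation.** 60,000 trials per cell, 34 against 33, bivariate-normal VAS with equal SD at both visits, age and gender unrelated to VAS, two-sided 5%. The t-test is on the change (65 df). The ANCOVA has treatment, baseline VAS, age and gender (62 df). The document does not give r, so 0.2 to 0.7 is an assumed range.

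*No true effect.* The t-test alone rejects in 4.9-5.0% of trials and ANCOVA alone in 4.8-5.0%.

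| r | 0.2 | 0.3 | 0.5 | 0.7 |
|---|---|---|---|---|
| At least one significant | 7.9% | 7.6% | 7.5% | 6.9% |

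A separate simulation with 34 per arm gave 8.3%, 8.0%, 7.3% and 7.0% at r = 0, 0.3, 0.5 and 0.7. For comparison, two independent tests would give 1 − 0.95² = 9.75%.

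*True effect of 20.3 points.* The plan does not say whether 25.8 is the SD of the change or of the score, so both readings are shown. Under the second, the SD of the change is 25.8 × √(2(1 − r)), which is 32.6 at r = 0.2 and 20.0 at r = 0.7.

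| r | 0.2 | 0.3 | 0.5 | 0.7 |
|---|---|---|---|---|
| **25.8 = SD of change** | | | | |
| t-test power | 88.7% | 88.6% | 88.7% | 88.4% |
| ANCOVA power | 97.9% | 96.9% | 94.7% | 91.6% |
| Tests disagree | 10.0% | 9.7% | 8.2% | 6.5% |
| of which ANCOVA only | 9.6% | 9.0% | 7.1% | 4.8% |
| **25.8 = SD of score** | | | | |
| t-test power | 70.9% | 76.4% | 88.8% | 98.4% |
| ANCOVA power | 88.3% | 90.0% | 94.7% | 99.0% |
| Tests disagree | 21.2% | 17.1% | 8.1% | 1.3% |

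The noncentral t distribution confirms the t-test rows: 88.7% under the first reading, and 70.8%, 76.5%, 88.7% and 98.4% under the second.

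**5. Secondary outcomes.** From the table in step 3, adjusting for an outcome's own baseline lowers the variance by 40% to 15% against a t-test on change, or by 4% to 49% against a t-test on discharge values, as r goes from 0.2 to 0.7.

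**The case against.** The best counter-argument is that a hierarchy is implied. The t-test is the general method, the ANCOVA is introduced as an addition with the stated purpose of adjustment, and the trial was sized without covariates. On that reading the t-test is primary and the ANCOVA supplementary. This is a reasonable reading, but not the only one. An unadjusted sample size is compatible with a later ANCOVA, and the ANCOVA sentence is the only one in Statistical methods that names VAS as the response.

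It is also fair to say that the 7-8% describes conduct the plan does not propose. That stands: it is a conditional figure, not the error rate of this design. The power and disagreement figures depend on an assumed correlation, equal SDs and the reading of 25.8, and they span a wide range. The direction depends on less. Step 3 shows that, apart from the few degrees of freedom spent on covariates, the ANCOVA variance does not exceed that of the change score even when the SDs differ.

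Finally, naming either test would cure the ambiguity, so choosing the ANCOVA is a preference for precision. The secondary-outcome point is likewise a suggestion. Both of these objections stand.

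**Conclusion.** The point holds. Two tests apply to the primary outcome and nothing in the document says which decides superiority; the cues towards the t-test are not a rule. Each test is valid alone, so the design is not broken, but the plan should be changed.

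The exposure is a type I error of about 7-8% if either test could carry the claim, and conflicting results in 6.5% to 10% of trials under the planned effect (1% to 21% if 25.8 is the SD of the score). These sizes assume 67 completers, normal data, equal SDs, non-prognostic age and gender, and r between 0.2 and 0.7. That two tests stand without a stated order needs none of these assumptions.

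**What to change.** Add to Statistical methods, before anyone sees outcome data by arm:

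> The single primary test of superiority is the ANCOVA of VAS change with treatment group, baseline VAS, age and gender, at two-sided 5%. The unadjusted t-test is supportive only.

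The ANCOVA is preferred because it is the more precise test and its covariates are already specified. At the same SD of change it needs no more than the planned 84 patients. The document is dated 2014 but cites 2017 sources, so it does not show how far data collection had gone; the sponsor should record when the choice was made.

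Optional: analyse each continuous secondary outcome with a meaningful baseline (WOMAC, EQ-5D, FIM, strength, ROM, proprioception) by ANCOVA with its own baseline as covariate. If this is declined, state whether the t-tests use changes or discharge values. Categorical outcomes keep the chi-square test, and the GPE needs no baseline covariate.

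The cost is SAP wording only: no new data and no more patients.

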### **Role of the funding source**

The funding sources has no controlling role in the study design, data collection, analysis, interpretation, or report writing. The corresponding author is responsible for the decision to submit the manuscript for publication.

### **Conflicting interests**

The authors declare that they have no competing interests.

### **Funding**

The work is supported by the Italian Ministry of Health for Conto Capitale 2012 (PCC-2012-2353895).

